4.2 Scientific Rationale for Study Design

AZD7442 is being evaluated for prophylaxis of COVID-19 and treatment of COVID-19 in adults. This Phase I study will provide information on the PK profile, SARS-CoV-2-neutralizing antibody titers and effect on viral load, as well as data on the safety and tolerability of AZD7442 and potential generation of ADAs to AZD7442 in pediatrics. This study will support the extrapolation of the efficacy and safety data observed in adults to children and determination of the therapeutic dose in children.

4.2.1 Rationale for Choice of Endpoints

The endpoints chosen for this Phase I PK/PD and safety study are consistent with those in AZD7442 studies in adults.

The primary study PK endpoints are those required to characterize the PK profile of AZD7442 following a single IM or IV dose administered to pediatrics aged \geq 29 weeks GA to < 18 years (Day 1 through Day 366). Pharmacokinetic sampling will be kept to a minimum due to the age of the population under study: one sample on Day 1 for participants receiving an IV infusion, one sample during the first 2 weeks for all participants (at either Day 4, 8, 11, or 15, spread across participants), then one sample at Day 31, 92, 183, and 366 (ie, the total number of samples per participant is up to 5 samples for IM administration and 6 samples for IV administration due to the additional sample taken at the end of the infusion on Day 1). Pharmacokinetic data will be analyzed by population methods and if data permit by non-compartmental analysis approach. This sampling scheme also enables serum AZD7442 concentration data to be obtained at the time points of primary efficacy endpoint evaluation for prophylaxis and treatment in the adult program. Pharmacokinetic profiles of AZD7442 are expected to be similar across the prophylaxis and treatment populations recruited because AZD7442 is cleared via nonspecific intracellular metabolism and will not be affected by binding to the exogenous target SARS-CoV-2. Therefore, PK data will be pooled across the cohorts within each age group.

The PD markers that are measured in this PK/PD and safety study will be used to support the assumption that the exposure-response relationship is similar for adults and children. In SARS-CoV-2 infected and non-infected children, the SARS-CoV-2 neutralizing antibody titer will be measured in a validated live neutralization assay. In addition, the neutralizing antibody titer will be correlated to the serum AZD7442 concentration. The correlation between drug level and neutralizing antibody titer in children will be compared to the correlation derived in adult serum samples.

The measures of viral load, disease progression or recovery, SARS-CoV-2 infections, and COVID-19-related death mirror the endpoints in the adult studies with AZD7442.

Adverse events associated with exogenous immunoglobulins as a class, ie, infusion reactions, hypersensitivity reactions, including anaphylaxis, and injection site reactions, typically manifest within minutes to hours, and rarely after 24 hours. For such events, the 24 hours of monitoring assigned to the sentinel dosing group should be sufficient for detection. The safety endpoints are standard endpoints for safety assessment and include incidence of treatment-emergent AEs, SAEs, and safety clinical laboratory measurements, with the addition of MIS-C as an AESI that is specific for SARS-CoV-2 infection in children. The presence of ADA and the potential impact of ADA on PK, PD, or safety will also be assessed.

The revised study duration of 366 -days will allow follow-up of dosed participants through approximately 4 AZD7442 half-lives, which is expected to provide sufficient safety follow-up and will also maximize the probability of detecting ADA to AZD7442.

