9.4.3 Pharmacodynamics

9.4.3.1 Secondary Endpoint: Neutralizing Antibody Titers

Samples will be collected for the evaluation of the functional inhibition of SARS-CoV-2 by AZD7442 concentrations in serum. Results will be listed for each participant and time point. Descriptive statistics for geometric mean titers and geometric mean fold rises will include number of participants, geometric mean, geometric SD, 95% CI, minimum, and maximum.

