### **3.3.8 Multiplicity/Multiple Comparisons**

No hypotheses are planned to be formally tested using inferential statistics in this study so multiplicity is not a concern.

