### 4.2 Endpoint Analyses

This section covers details related to the endpoint analyses such as primary, secondary, other endpoints. Sensitivity analyses are done by repeating the endpoint analyses using a sensitivity analysis set if indicated in [Table 2](#). The analysis sets shown are applicable to the tables of the endpoints. Listings may utilize other sets. All endpoint analyses will be descriptive qualitative or quantitative summaries.

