### **4.2.3 Secondary Endpoint – All Cohorts**

#### **4.2.3.1 SARS-CoV-2 neutralizing antibodies**

To evaluate the PD of AZD7442 after a single IM or IV dose, titers of SARS-CoV-2 neutralizing antibodies will be listed for the SAF and summarized for the SES at each time point.

Descriptive statistics for gmean titers (GMT) and geometric mean fold rises will include number of participants, gmean, gSD, 95% CI for the gmean, minimum, and maximum.

The GMTs for nAbs will be calculated for all participants in the SES as the antilogarithm of  $\Sigma(\log_2 \text{transformed titer}/n)$ , ieas the antilogarithm transformation of the mean of the log-transformed titer with base 2, where n is the number of participants with titer information. The gSD for GMT will be calculated as the antilogarithm transformation of the standard deviation of the log-transformed titer. The 95% CI will be calculated as the antilogarithm transformation of the upper and lower limits for a two-sided CI for the mean of the log-transformed titers.

Summary tables will be generated by cohort and route of IMP administration, and separately by cohort, route of administration and COVID-19 vaccination status at baseline (as captured in the eCRF).

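### Comparing titer–concentration correlations between children and adults cannot show a proportional titer deficit in children, and no SAP analysis would show it either

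*Protocol*

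**What the plan says.** Protocol 4.2 gives the purpose of the study: "This study will support the extrapolation of the efficacy and safety data observed in adults to children". Protocol 4.2.1 gives the pharmacodynamic markers a part in this. They "will be used to support the assumption that the exposure-response relationship is similar for adults and children". Two steps follow there. In children, "the neutralizing antibody titer will be correlated to the serum AZD7442 concentration". Then: "The correlation between drug level and neutralizing antibody titer in children will be compared to the correlation derived in adult serum samples".

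The protocol does not name the coefficient, the scale, the adult samples or the agreement that would count as similar.

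The analysis sections do not take this up. Protocol 9.4.3.1 and SAP 4.2.3.1 both summarize titers alone (SAP: "Descriptive statistics for gmean titers (GMT) and geometric mean fold rises will include number of participants"). SAP 4.2.3.2 adds plots of titer against time by anti-drug antibody status. Neither document's analysis section relates titer to concentration or to adult titers. The SAP also states that "All endpoint analyses will be descriptive qualitative or quantitative summaries" and that "No hypotheses are planned to be formally tested using inferential statistics in this study".

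**The concern.** Exposure-response is similar if the same serum concentration gives about the same neutralization in a child as in an adult. The departure that matters most for extrapolation is a lower titer at the same concentration. A correlation coefficient measures how tightly points lie around a line within one group. It does not measure how high the line sits, so two groups can share a coefficient and differ several-fold in titer per unit of drug.

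The coefficient also rises with the spread of concentrations. Two groups on the same line can therefore have different coefficients because one was dosed or sampled over a wider range. At stake is whether the similarity statement rests on a quantity that bears on it.

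**Working it through.** The documents give no figure for this comparison, so there is nothing of the plan's own to reproduce.

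**Inputs from the documents**
- Post-dose titers and concentrations in children at Days 31, 92, 183 and 366, that is 30, 91, 182 and 365 days after dosing (Protocol Table 3).
- Half-life: 366 days is about 4 half-lives (Protocol 4.2.1), so 366/4 = 91.5 days.
- Children: 46 in the full analysis set (SAP 2). Neonates give no neutralizing-antibody samples (Protocol 8.5.1), so 46 is an upper limit.
- Adult Phase I doses: 300 to 3000 mg (SAP Table 5).

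**Assumptions not in the documents:** 200 adult samples; one independent pair per participant; slope 1 on log2 scales; between-subject SD of log2 concentration 0.6; residual SD of log2 titer 0.5 to 1.5 (1 unless stated).

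**1. Invariance.** For k > 0, corr(X, kY) = corr(X, Y), and corr(log X, log Y + log k) = corr(log X, log Y). A rank correlation is also unchanged, because the ranks are. In one simulated data set with child titers multiplied by 1, 1/2 and 1/4:

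| Titer ratio | Pearson, logs | Pearson, raw | Spearman |
|---|---|---|---|
| 1.00 | 0.8317 | 0.5598 | 0.8341 |
| 0.50 | 0.8317 | 0.5598 | 0.8341 |
| 0.25 | 0.8317 | 0.5598 | 0.8341 |

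**2. What sets the coefficient.** With slope b, concentration variance V and residual variance s² (log2 scales), r = √[b²V/(b²V + s²)]. The level of the line does not appear.
- The four sampling times lie 0.328, 0.995, 1.989 and 3.989 half-lives after dosing. Their variance is 1.91, so V = 1.91 + 0.6² = 2.27.
- With b = 1 and s = 1, r = √(2.27/3.27) = 0.83.

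**3. Flag rates, 3,000 runs per setting.** The two coefficients were compared by Fisher z, with standard error √[1/(46−3) + 1/(200−3)] = 0.168. The alternative was a group term in a regression of log2 titer on log2 concentration. Ranges cover 46 or 100 children and residual SD 0.5 to 1.5.

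| True child titer at equal concentration | Correlations flagged | Regression flagged |
|---|---|---|
| Same | 3% to 5% | 4.5% to 5.4% |
| 2-fold lower | 3% to 5% | 98% to 100% |
| 4-fold lower | 3% to 5% | 100% |

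**4. Same relationship, different range.** Adult doses of 300, 1000 and 3000 mg in equal shares add a log2 variance of 1.84. Then V = 2.27 + 1.84 = 4.11 and the adult r = √(4.11/5.11) = 0.90, against 0.83 in children. A difference was flagged in 29% of runs with 46 children and 53% with 100.

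The size depends on which adult samples are used. For the adult pre-exposure study's sampling days in SAP Table 5 (28, 57, 91, 182 and 365, one dose), the variance over time is 1.77, so V = 1.77 + 0.36 = 2.13 and r = √(2.13/3.13) = 0.82. That is almost the children's value.

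**5. What the correlation does detect** (46 children, residual SD 1)
- Child slope halved: r falls to 0.60, flagged in 84%. Slope zero: flagged in 100%.
- Titers floored at an assumed quantification limit about 4-fold below the adult mean: r is 0.81 with no deficit, 0.76 with a 2-fold deficit (flagged in 8%) and 0.65 with a 4-fold deficit (flagged in 57%).

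In the floored runs a regression that ignored the floor gave ratios of 0.58 and 0.38 where the truth was 0.50 and 0.25. Censoring therefore matters to the replacement too.

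**6. Precision of the ratio.** The approximate 95% CI factor is 2^[1.96 × s × √(1/46 + 1/200)]: 1.12, 1.25 and 1.40 for s = 0.5, 1 and 1.5.

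**The case against.** **The wording may be loose.** Protocol 4.2.1 is a rationale section and names no coefficient or test. If the sponsor means the fitted titer–concentration relationship, comparing it between groups would show a shift. That reading is open, but no document states it, and it would need much the same edit: say that slope and titer at a given concentration are what is compared.

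**The study is descriptive.** This stands. No decision rule is stated, so one cannot say that the plan will read no difference as similarity. But 4.2.1 does intend to draw support for similarity, and a ratio with a confidence interval is itself descriptive.

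**Stronger readings a reader might infer, which the documents do not support**
- *The check supports similarity whether or not it is true.* It fails only for a proportional shift without censoring. A flatter slope, more scatter or an assay floor would move the coefficient.
- *Adults followed for a shorter time would make a false difference near certain.* That needs a cutoff such as Day 183. SAP Table 5 lists adult PK sampling to 360 or 365 days in four of the five adult studies; only the study in hospitalized adults stops earlier, at Day 90. Adult titer days are not given.
- *Extrapolation rests on this comparison.* Doses were chosen by population PK simulation to match adult exposure (Protocol 4.3), and PK is a co-primary objective (Protocol 3). The titer comparison is supporting evidence.

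**A child/adult shift need not come from the drug.** This also stands. Cohort 2 is infected at entry, COVID-19 vaccination is allowed before and during the study (Protocol 5.2 and 6.5.1), and Protocol 8.5.4.1 allows live-virus or pseudovirus assays although 4.2.1 speaks of a live assay. The replacement has to deal with each of these.

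**Conclusion.** The point holds in a limited form. Read as a comparison of correlation coefficients, the check in Protocol 4.2.1 carries no information about a proportional titer deficit when titers are not censored. This is algebra and rests on no assumed value. The check is also confounded by concentration range, with a size that depends on adult data the documents do not specify: about 29% false differences with 46 children in the 300 to 3000 mg illustration, and little effect under the adult pre-exposure sampling days. Those figures, the regression's 98% to 100% detection and its interval width rest on the assumed noise, 200 adult samples and independent pairs. The detection rates also assume that all measured titer comes from the drug.

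The practical gap is in the SAP. It carries neither the stated comparison nor any other that would catch a proportional deficit. This affects supporting pharmacodynamic evidence, not the primary endpoints, and should be corrected.

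**What to change.** In Protocol 4.2.1, replace the comparison of correlations. In SAP 4.2.3.1, add:

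- A repeated-measures regression of log2 titer on log2 AZD7442 concentration, with a child/adult term and its interaction with concentration.
- The child/adult ratio of predicted titer at one or two fixed concentrations (for example the adult geometric mean at Day 183), with a confidence interval. Read it descriptively or against a range the sponsor sets in advance.
- The adult studies and samples used, and the same neutralization assay in both groups.
- Titers below the quantification limit treated as censored. Participants with no quantifiable post-dose titer should be kept in this model; the definition of the SARS-CoV-2 nAb Evaluable Analysis Set leaves them out.
- Adjustment for, or restriction by, baseline titer or serostatus, infection and COVID-19 vaccination, so that antibody from other sources is not read as a drug effect.
- A statement that neonates give no neutralizing-antibody samples and are not covered.

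The cost is some wording and a modest amount of analysis. It needs no new sampling in children and uses the adult serum data that 4.2.1 already relies on. The downside for the sponsor is that the similarity statement can now fail.

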4.2.2 Rationale for Study Population

Children of all ages are susceptible to SARS-CoV-2 infection and COVID-19 but many children will not develop severe disease; therefore, Cohorts 1 and 2 (prophylaxis and treatment of mild to moderate disease) will only include participants who have an underlying condition that increases their risk for developing severe COVID-19. Participants in Cohort 3 (treatment of severe disease) require urgent treatment, so they are not required to have any pre-existing health conditions.

Participants will be stratified by age (\geq 29 weeks GA to < 1 year; \geq 1 year < 6 years; \geq 6 years to < 12 years; \geq 12 years to < 18 years) to ensure that data are obtained from all pediatric age groups in the study. In addition, the youngest age category has been further stratified into 2 subgroups (\geq 29 weeks GA to < 1 month and \geq 1 month to < 1 year), to ensure that neonates are represented as they are particularly susceptible to COVID-19.

4.2.3 Participant Input into Design

Not applicable for a PK study.

4.3 Justification for Dose

The IM and IV doses to be investigated in this study were determined by simulations using the population PK model developed based on available data from the adult studies. The model used for the simulations included a weight-based allometric scaling of CL and volume as well as an age-based maturation function for CL to represent the entire range of the pediatric population. A dosing by body weight bands approach was chosen. Four weight band categories were considered: \geq 1.5 to < 5 kg; \geq 5 to < 15 kg; \geq 15 to < 40 kg and \geq 40 kg. The IM and IV doses in the respective body weight categories were selected so the predicted exposure in each weight category matches as closely as possible the exposure in adults at the highest authorized or investigated (if indication not yet approved) doses in each indication at the time of recruitment initiation in each cohort. In particular, pediatric prophylaxis doses

were selected such that the AZD7442 predicted serum concentrations were within the same range as adults at 6 months. The doses to be investigated in each weight category in the different indications are presented in **Table 6**. AZD7442 was investigated at doses up to 3000 mg administered IV in adults in the Phase I FTIH study (D8850C00001), which is 5-fold higher than the maximum adult dose investigated in the Phase III adult studies.

Intramuscular injection is the preferred route of administration for outpatients (prophylaxis or treatment of mild to moderate disease) but for some participants, the IV route of administration will be more appropriate (see criteria for IV administration specified in the inclusion criteria in Section 5.1). Therefore, the IV route of administration has also been included for eligible participants in Cohorts 1 and 2. For patients who are hospitalized with severe COVID-19 in Cohort 3, IV administration is the route investigated in the clinical adult studies.

Table 6 **Planned Doses in the Different Indications in the Pediatric PK/PD/Safety Study**

Participant weight range	Prophylaxis (matching adult dose of 600 mg IM)		Treatment – Outpatient (matching adult dose of 600 mg IM)		Treatment – Inpatient (matching adult dose of 600 mg IV)
	Planned IM dose (mg)	Planned IV dose (mg)	Planned IM dose (mg)	Planned IV dose (mg)	Planned IV dose (mg)
≥ 1.5 to < 5 kg	60	50	60	50	60
≥ 5 to < 15 kg	150	110	150	110	150
≥ 15 to < 40 kg	NA ^a	300	NA ^a	300	400
≥ 40 kg	600	440	600	440	600

^a In participants who weigh ≥ 15 to < 40 kg, IM dosing is not feasible for the treatment indication due to the maximum volume required for injection.

IM, intramuscular; IV, intravenous; PD, pharmacodynamic; PK, pharmacokinetic.

4.4 End of Study Definition

For the purpose of Clinical Trial Transparency, the definition of the end of the study differs under FDA and EU regulatory requirements:

European Union requirements define study completion as the last visit of the last subject for any protocol related activity.

Food and Drug Administration requirements define two completion dates:

Primary Completion Date – the date that the final participant is examined or receives an intervention for the purposes of final collection of data for the primary outcome measure, whether the clinical study concluded according to the pre-specified protocol or was terminated. In the case of clinical studies with more than one primary outcome measure with

different completion dates, this term refers to the date on which data collection is completed for all of the primary outcomes.

Study Completion Date – the date the final participant is examined or receives an intervention for purposes of final collection of data for the primary and secondary outcome measures and AEs (for example, last participant’s last visit), whether the clinical study concludes according to the pre-specified protocol or is terminated.

A participant is considered to have completed the study if he/she has completed all phases of the study including the last scheduled procedure shown in the SoA in Section 1.3.

5 STUDY POPULATION

Prospective approval of protocol deviations to recruitment and enrollment criteria, also known as protocol waivers or exemptions, is not permitted.

5.1 Inclusion Criteria

Participants are eligible to be included in the study only if all the following criteria apply:

Age and Weight

- 1 Participant must be aged \geq 29 weeks GA to $<$ 18 years of age at the time of signing the informed consent (see Appendix A 3 for procedures around informed consent).
- 2 Participant must weigh a minimum of 1.5 kg.

Type of Participant and Disease Characteristics

COHORT 1: Participants who do not have COVID-19 and have not knowingly been exposed to a SARS-CoV-2 positive individual (pre-exposure prophylaxis):

- 3 At increased risk of severe COVID-19 for any of the following reasons:
 - (a) Immunocompromised state
 - (b) One or more comorbid conditions that increase the risk of severe COVID-19, eg, cardiovascular disease, including heart disease since birth, malignancy, chronic kidney disease, and genetic, neurologic, or metabolic conditions.
- 4 Medically stable defined as disease not requiring significant change in therapy or hospitalization for worsening disease during the one month prior to enrollment, with no acute change in condition at the time of study enrollment as judged by the Investigator.
- 5 Documented negative SARS-CoV-2 RT-PCR test collected \leq 3 days prior to Day 1 or a negative rapid SARS-CoV-2 antigen test at screening.
- 6 Prior to enrollment, participants must not have had COVID-19 symptoms (Table 13) within 10 days of dosing.

7 Increased risk for SARS-CoV-2 infection, defined as those whose locations or circumstances put them at appreciable risk of exposure to SARS-CoV-2 and COVID-19, based on available risk assessment at time of enrollment.

COHORT 2: Participants with COVID-19 and mild to moderate symptoms (treatment):

8 At increased risk of severe COVID-19 for any of the following reasons:

- (a) Immunocompromised state
- (b) One or more comorbid conditions that increase the risk of severe COVID-19 (see list in 3[b])

9 Medically stable defined as disease not requiring significant change in therapy or hospitalization for worsening disease during the one month prior to enrollment, with no acute change in condition at the time of study enrollment as judged by the Investigator.

10 Documented positive SARS-CoV-2 RT-PCR test collected \leq 3 days prior to Day 1 or a positive rapid SARS-CoV-2 antigen test at screening.

11 Participants who are symptomatic must be dosed with IMP no more than 7 days from self-reported or observed onset of COVID-19-related symptoms or measured fever, defined as the self-reported date of first reported sign/symptom from the list in [Table 13](#). One or more COVID-19 signs/symptoms must also be present within 24 hours prior to Day 1 to be eligible for inclusion.

12 Oxygenation saturation of \geq 92% obtained at rest by study staff within 24 hours prior to Day 1, unless the potential participant regularly receives chronic supplementary oxygen for an underlying lung condition.

Note that Cohort 2 will only be included if the indication is progressed in adults.

COHORT 3: Participants with severe COVID-19 (treatment):

13 Patients hospitalized with COVID-19 with a time between onset of symptoms and dosing AZD7442 of \leq 7 days

14 Documented positive SARS-CoV-2 RT-PCR test collected \leq 3 days prior to Day 1 or a positive rapid SARS-CoV-2 antigen test at screening.

15 Spontaneous blood ALT/AST levels \leq 5 times the ULN

16 Glomerular filtration rate \geq 30 mL/min/1.73 m²

Note that Cohort 3 will only be included if the indication is progressed in adults.

Route of Administration:

Participants will receive IM AZD7442 unless they meet any of the following criteria for IV administration:

- 17 The participant has severe COVID-19
- 18 IM dosing is contraindicated due to:
 - (a) Thrombocytopenia (< 120000 cells/mm³)
 - (b) Coagulation defects
 - (c) Any other condition that would compromise the absorption of AZD7442 or safety of the participant (eg, hypovolemic shock, myopathy, muscular atrophy, active infection other than SARS-CoV-2, cellulitis, and dermatitis at the injection site).
- 19 Any other participant for whom the enrolling physician considers an IV infusion the most appropriate route of administration.

Informed Consent

- 20 Provision of a signed and dated written informed consent form prior to any mandatory study specific procedures, sampling, and analyses. Informed assent is to be provided by participants who are capable of forming an opinion and assessing the information given to him or her; informed consent must be provided by the participant's legal guardian.

